2.4.4.4 Multiplicity issues

No adjustments for multiplicity are planned for this Phase 2a study. More specifically, no adjustments will be made in comparing the two treatment groups based on the secondary efficacy endpoints and no adjustments will be made for the subgroup analyses. All reported p-values will be nominal.

2.4.5 Analyses of safety data

The summary of safety results will be presented by treatment group.

General common rules

All safety analyses will be performed on the safety population as defined in [Section 2.3.2](#), unless otherwise specified, using the following common rules:

- Safety data in patients who do not belong to the safety population will be listed separately.
- The baseline value is defined as the last available value prior to the first dose of the IMP.
- The potentially clinically significant abnormality (PCSA) values are defined as abnormal values considered medically important by the Sponsor according to predefined criteria/thresholds based on literature review and defined by the Sponsor for clinical laboratory tests, vital signs, and ECG (PCSA version dated May 2014, see [Appendix A](#)).
- PCSA criteria will determine which patients had at least 1 PCSA during the treatment-emergent adverse event period, taking into account all evaluations performed during the treatment-emergent adverse event period, including nonscheduled or repeated evaluations. The number of all such patients will be the numerator for the on-treatment PCSA percentage.
- The treatment-emergent PCSA denominator by group for a given parameter will be based on the number of patients assessed for that given parameter in the TEAE period by treatment group on the safety population.
- For quantitative safety parameters based on central laboratory/reading measurements, descriptive statistics will be used to summarize results and change from baseline values by visit and treatment group. Summaries will include the endpoint value. The endpoint value

is commonly defined as the value collected at or just prior to the last dose date +14 days, or at the end of treatment visit, whichever comes later. If this value is missing, this endpoint value will be the closest value prior to the last dose intake. The worst value is defined as the nadir and/or the peak post-baseline (up to last administration of IMP) according to the direction (minimum or maximum) of the abnormality as defined in the PCSA list.

- The analysis of the safety variables will be essentially descriptive and no systematic testing is planned.

All safety values including unscheduled measurements will be assigned to the appropriate safety analysis visit window defined in [Section 2.5.4](#).

2.4.5.1 Analyses of adverse events

Generalities

The primary focus of adverse event reporting will be on TEAEs. Pre-treatment and post-treatment adverse events will be described separately.

If an adverse event date/time of onset (occurrence, worsening, or becoming serious) is incomplete, an imputation algorithm will be used to classify the adverse event as pre-treatment, treatment-emergent, or post-treatment. The algorithm for imputing date/time of onset will be conservative and will classify an adverse event as treatment emergent unless there is definitive information to determine it is pre-treatment or post-treatment. Details on classification of adverse events with missing or partial onset dates are provided in [Section 2.5.3](#).

Adverse event incidence tables will present the number (n) and percentage (%) of patients experiencing an event by treatment group. Multiple occurrences of the same event in the same patient will be counted only once in the tables within a treatment phase. The denominator for computation of percentages is the safety population within each treatment group. Sorting will be based on results for the SAR440340 group by the following orders:

- Tables presented by SOC: sorted by internationally agreed SOC order
- Tables presented by PT: sorted by decreasing frequency of PT
- Tables presented by SOC and PT: sorted by internationally agreed SOC order and decreasing frequency of PT within SOC

Analysis of all TEAEs

The following TEAE summaries will be generated for the safety population.

- Overview of TEAE, summarizing number (%) of patients with any
 - TEAE
 - Severe TEAE

- Serious TEAE
- TEAE leading to death
- TEAE leading to permanent treatment discontinuation
- All TEAEs by primary SOC
- All TEAEs by PT
- All TEAEs by primary SOC and PT
- All TEAEs related to SAR440340 or matching placebo by primary SOC and PT
- All TEAEs by maximal severity, presented by primary SOC and PT
- Listing of all TEAEs

Analysis of all treatment emergent SAEs

- All treatment-emergent SAEs by primary SOC and PT
- All treatment-emergent SAEs by PT
- All treatment-emergent SAEs related to SAR440340 or matching placebo by primary SOC and PT
- Listing of all treatment-emergent SAEs

Analysis of all TEAEs leading to permanent treatment discontinuation

- All TEAEs leading to permanent treatment discontinuation by primary SOC and PT
- All TEAEs leading to permanent treatment discontinuation by PT
- Listing of all AEs leading to permanent treatment discontinuation

Analysis of AESI

A summary of number of patients with any TEAE by AESI category (defined by the search criteria in [Section 2.1.4.1](#)) will be generated. In addition, for each AESI category the following will be provided:

- All TEAEs by PT
- Overview summary including
 - Number (%) of patients with any TEAE
 - Number (%) of patients with any SAE (regardless of treatment emergent status)
 - Number (%) of patients with any treatment-emergent SAE
 - Number (%) of patients with any AE leading to death
 - Number (%) of patients with any TEAE leading to permanent treatment discontinuation
 - Number (%) of patients with any TEAE related to IMP reported by investigator

- Number (%) of patients with any TEAE by maximum intensity, corrective treatment, and final outcome
- Number of TEAE adjusted by the exposure duration

For categories with at least 5 events in at least one treatment group, K-M plots of time to first event will be provided to depict the course of onset over time.

Analysis of pre-treatment and post-treatment adverse events

Listings will be provided for all pre- and post-treatment AEs. The following summaries may be generated if the number of events is large enough:

- All pre-treatment AEs by primary SOC and PT
- All pre-treatment SAEs by primary SOC and PT
- All pre-treatment AEs leading to treatment discontinuation by primary SOC and PT
- All pre-treatment AEs leading to death by primary SOC and PT
- All post-treatment AEs by primary SOC and PT
- All post-treatment SAEs by primary SOC and PT
- All post-treatment AEs leading to death by primary SOC and PT

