9.4.2 Safety analyses

The summary of safety results will be presented by treatment group. All safety analyses will be performed on the mITT population using the following common rules:

The baseline value is defined generally as the last available value before the first dose of IMP.

Table 15 - Safety analyses

Endpoint	Statistical Analysis Methods
AE, SAE, AE leading to discontinuation	
Adverse event incidence tables will present by system organ class (SOC) (sorted by internationally agreed order), high-level group term (HLGT), high level term (HLT) and preferred term (PT) sorted in alphabetical order for each treatment group, the number (n) and percentage (%) of patients experiencing an AE. Multiple occurrences of the same event in the same patient will be counted only once in the tables within a treatment phase. The denominator for computation of percentages is the safety population within each treatment group.
 
Proportion of patients with at least one TEAE, serious TEAE, and TEAE leading to discontinuation of the study will be tabulated by treatment group. In addition TEAEs will be described according to maximum intensity and relation to the study drug. Serious AEs and AEs leading to study discontinuation that occur outside the treatment-emergent period will be summarized separately.

AESI	
The following summaries will be generated:
 
 1. Incidence of each AESI will be tabulated by treatment group. 2. The time-to-first event analyzed using K-M methods and displayed as K-M plots (cumulative incidence (%) versus time based on K-M estimates) will be provided to depict the course of onset over time. When TEAE start date or worsening date is partially available, the maximum of the earliest possible TEAE start date and the treatment start date will be used. When TEAE start date or worsening date is completely missing, the treatment start date will be used. 3. An overview summary of the number (%) of patients with 
 - any TEAE - any serious AE (regardless of treatment-emergent status) - any treatment-emergent SAE - any AE leading to death - any TEAE leading to permanent study drug discontinuation - any TEAE by maximum intensity, corrective treatment, and final outcome - cumulative incidence at specified time points (K-M estimates at Week 1, 4, 12, 24, 52 and 72) 
Definitions of AESIs and the method to identify AESIs will be specified in the SAP.

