1.3 DETERMINATION OF SAMPLE SIZE

To assess the power of the primary efficacy endpoint the annualized rate of moderate-to-severe AECOPD, we assume

- Average of 1.0 to 1.5 AECOPD per year in the placebo group of this study population enriched for severity and high risk of AECOPD.
- The number of AECOPD follows a negative binomial distribution with dispersion parameter 1.5 for all the groups.
- A Wald-test is used to test whether the risk ratio is 1 with 2-sided 5% significance level.
- Patients will be treated with a minimum of 24 weeks and a maximum of 52 weeks depending on their study entry times. The monthly cumulative patient accruals are assumed to be 1, 5, 10, 25, 50, 90, 150, 210, 270, 335 and 340 for an eleven (11)-month accrual period.

- Cumulatively, 9%, 15% and 20% of patients drop out of the study due to discontinuation or other reasons by 12, 24 and 52 weeks after study entry.
- Patients are randomized to the treatment group and the placebo group with a 1:1 ratio.

With these assumptions and 170 patients per group (340 patients in total), the study will yield 81.6% to 88.8% powers with risk reduction equal to 45% in rate of AECOPD and the placebo rate ranging from 1.0 to 1.5 per year. To obtain at least 80% power, the minimum risk reduction is from 44.2% to 40.6%. The minimum detectable risk reduction (i.e. with 50% power) is from 32.7% to 30.0%. See the table below for more details.

Table 1 - Power calculation for various AECOPD event rates in the placebo group

Placebo rate	Power for certain Risk Reduction (RR)			Minimum RR for certain power	
	RR=40%	RR=45%	RR=50%	Power=80%	Power=50%
1.0	69.9%	81.6%	90.3%	44.2%	32.7%
1.2	74.1%	85.2%	92.9%	42.5%	31.4%
1.5	78.5%	88.8%	95.2%	40.6%	30.0%

RR: risk reduction

Based on the accrual and drop-out assumptions, the mean exposure time is 35.5 (\pm 12.8) weeks. Since we use variable follow-up times for patients entering at different times, the power will depend on the actual accrual rates and the drop-out rates. We will closely monitor these rates. If the accrual rates are significantly lower than planned and/or the drop-out rates are higher than expected, the minimum treatment period may be extended to achieve the desired amount of total exposure. The maximum treatment period of 52 weeks will not be changed.

To assess the key secondary efficacy endpoint, the change from baseline to Week 24 in pre-bronchodilator FEV1, we assume that:

[figure not shown]

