1.4 STUDY PLAN

Please refer to Section 1.2 of the study protocol for study flow chart. The graphical study design is provided in [Figure 1](#)

Figure 1 – Graphical Study

Design

★ Treatment consisting of 2 injections of 1.5 mL each of SAR440340 or placebo

¹ Variable treatment period determined by either completion of a 52 week treatment duration or the end of treatment of the last patient completing planned treatment (EOT visit), whichever occurs earlier

² End of Treatment (EOT) visit to occur 2 weeks after last administration of IMP

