2.1.4 Safety endpoints

The safety analysis will be based on the reported adverse events (AEs) and other safety information, such as clinical laboratory data, vital signs, electrocardiogram (ECG), etc.

Observation period

The observation period will be divided into 4 epochs:

- The **screening** epoch is defined as the time from the signed informed consent date up to the first administration of the IMP.
- The **treatment** epoch is defined as the time from the first administration of the IMP to the last administration of the IMP + 14 days.
- The **residual treatment** epoch is defined as the time from the last administration of the IMP + 15 days to the last administration of the IMP + 154 days.
- If applicable, the **post-treatment** epoch is defined as the time from the last administration of the IMP + 155 days to the patient's end of study (defined as last protocol-planned visit or the resolution/stabilization of all serious adverse events and adverse events with pre-specified monitoring).

The treatment-emergent adverse event (TEAE) period will include both **treatment** and **residual treatment** epochs.

The on-study observation period is defined as the time from the first administration of the IMP to the end of the study.

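### SAP 2.4.5.1 leaves out, undeclared, the protocol's fixed-week Kaplan-Meier AESI estimates; the tabulated AESI risks are then crude percentages tied to no stated week, and biased between arms only if drop-out differs by arm

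*SAP*

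**What the plan says.** **Protocol 9.4.2, Table 15, AESI row.** It plans incidence tables by arm, K-M plots of time to first event with no minimum number of events, and an overview that ends with "cumulative incidence at specified time points (K-M estimates at Week 1, 4, 12, 24, 52 and 72". The row leaves AESI definitions and search methods to the SAP. It does not leave open whether these estimates are produced.

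**SAP 2.4.5.1, Analysis of AESI.** It repeats most of the protocol's overview items: any TEAE, serious events, deaths, discontinuations, intensity and outcome. It has no fixed-week estimates. On K-M output it says: "For categories with at least 5 events in at least one treatment group, K-M plots of time to first event will be provided". It adds one item for each category: "Number of TEAE adjusted by the exposure duration".

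**SAP 2.4.5.1, Generalities.** "The denominator for computation of percentages is the safety population within each treatment group", whatever each patient's follow-up.

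**SAP 1.5 and 1.6.** Section 1.5 records two changes to the protocol's statistics, the high-eosinophil population and the SGRQ responder endpoint. Section 1.6 is marked not applicable. The AESI change appears in neither.

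**Follow-up.** SAP 1.3 plans treatment for a "minimum of 24 weeks and a maximum of 52 weeks". SAP 1.4 has the end-of-treatment "visit to occur 2 weeks after last administration of IMP". SAP 2.1.4 ends the treatment-emergent period with the residual treatment epoch, which is "the time from the last administration of the IMP + 15 days to the last administration of the IMP + 154 days".

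**The concern.** AESIs are the harms that the sponsor singled out: serious and opportunistic infection, hypersensitivity, liver disorder, malignancy and others. A percentage of all treated patients is easy to read as a risk, but here patients are watched for very different lengths of time. A reader cannot say by which week the stated percentage of patients had the event. An arm whose patients leave earlier is watched for less time and can look safer for that reason alone.

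K-M estimates at fixed weeks, as the protocol planned, deal with both problems when censoring is non-informative. The threshold of 5 events removes even the plot where counts are low, for example 4 of 170 patients against 0. Rare but important categories such as malignancy, opportunistic infection or anaphylaxis could fall there; the documents give no expected rates.

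**Working it through.** **1. Reproduce the plan.** Inputs from SAP 1.3: cumulative monthly accrual of "1, 5, 10, 25, 50, 90, 150, 210, 270, 335 and 340 for an eleven (11)-month accrual period"; drop-out of 9%, 15% and 20% by Weeks 12, 24 and 52 (linear in between); planned duration = min(52, 24 + weeks from entry to the end of accrual), with entry uniform within each month. Simulated mean planned duration is 40.2 weeks, and mean exposure after drop-out is 35.5 weeks (SD 12.8). The plan states 35.5 (±12.8). Power at a 45% reduction is 81.7, 85.3 and 88.8%, against the stated 81.6, 85.2 and 88.8%. The inputs are therefore read as the sponsor meant them.

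**2. Treatment-emergent window.** The last dose is 2 weeks before end of treatment, and the window closes 154 days (22 weeks) after it.
- Shortest planned: 24 − 2 + 22 = 44 weeks.
- Longest planned: 52 − 2 + 22 = 72 weeks.
- Discontinuers: as little as about 22 weeks if followed to the end of the window, and less if they leave the study.

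**3. Numbers at risk.** About 38 of 340 patients have a 52-week plan. With 80% retained, about 31 are observed to Week 72, or about 15 per arm. About 229 of 340 are observed to Week 52 if drop-outs leave the study.

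**4. Crude risk under the planned drop-out.** Assumption: constant hazard h, because the documents give no AESI rate. With Week 52 risk p, h = −ln(1 − p)/52. Risk by Week t is 1 − exp(−ht). The expected crude percentage is the mean of 1 − exp(−hw) over patients' windows w. Two cases bracket the truth: drop-outs leave the study at once (mean observation 51.9 weeks), or all are followed to last dose + 154 days (35.5 + 20 = 55.5 weeks).

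| Week 52 risk | Week 72 risk | Crude, drop-outs leave | Crude, drop-outs followed | Shortfall against Week 72 |
|---|---|---|---|---|
| 5% | 6.9% | 5.0% | 5.3% | 27% and 22% |
| 10% | 13.6% | 9.9% | 10.6% | 27% and 22% |
| 20% | 26.6% | 19.7% | 21.1% | 26% and 21% |

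Rounding planned durations down to whole two-week dosing cycles moves the middle row only to 9.8% and 10.5%.

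**5. Unequal drop-out, equal hazards.** The drop-out curve is scaled by 1.5 (30%) or 2.0 (40%) on drug and by 0.5 (10%) on placebo. These imbalances are assumed; the plan has 20% in both arms. The percentages shown are for a 10% Week 52 risk.

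| Drop-out, drug vs placebo | Drop-outs leave | Drop-outs followed |
|---|---|---|
| 30% vs 10% | 9.1% vs 10.7%, ratio 0.85 | 10.2% vs 11.0%, ratio 0.92 |
| 40% vs 10% | 8.4% vs 10.7%, ratio 0.78 | 9.7% vs 11.0%, ratio 0.88 |

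The true ratio is 1 throughout. The ratios barely move across Week 52 risks of 5 to 20%.

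**6. Does the exposure-adjusted count fill the gap?** It counts events, not patients with an event by a given week. SAP 2.4.3.1 ends IMP exposure at last dose + 14 days, while treatment-emergent events count to + 154 days. If that exposure is the denominator, events from 55.5 weeks are divided by 35.5 weeks, a factor of 55.5/35.5 = 1.56. The factor depends on drop-out. The plan loses 40.2 − 35.5 = 4.7 weeks per patient. At 30% drop-out, exposure is 40.2 − 1.5 × 4.7 = 33.15 weeks and the factor is 53.15/33.15 = 1.60. At 10% it is 40.2 − 0.5 × 4.7 = 37.85 weeks and 57.85/37.85 = 1.53. The ratio between arms would shift by 1.60/1.53, about 5% upward, with no true difference.

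**The case against.** The case for leaving the SAP alone has real strength.

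- **Crude percentages are not new.** A reader might infer that the SAP swapped K-M for crude n (%). It did not: Table 15 already tabulates incidence with the safety population as denominator. What went is the fixed-week estimates and the plots for sparse categories.
- **K-M survives above the threshold.** A K-M curve shows risk by week and allows for censoring. The objection that risk is tied to no week therefore applies to the tables, and to all patient-risk output only below 5 events per arm. This stands, although a curve is not a tabulated estimate with an interval.
- **The 44 to 72 week spread does not itself bias the comparison.** It follows calendar entry, which concurrent 1:1 randomization should balance. This stands.
- **A general understatement of about a quarter is not supported.** That figure appears only against Week 72, which few patients reach. Against Week 52 the gap nearly vanishes.
- **Discontinuers are meant to be followed.** Protocol 4.1 and 7.1.1 ask them to attend remaining visits and safety follow-up. The milder ratios, 0.92 and 0.88, apply if this succeeds.
- **Other outputs help.** The SAP gives exposure in patient-years, withdrawals by arm and timing, liver abnormalities by duration of exposure, and full listings. None gives a patient risk by a stated week for an AESI.
- **Safety analysis is descriptive** in a Phase 2a trial. This limits the stakes but does not explain an undeclared change.

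**Conclusion.** The point holds as a departure from the protocol that the SAP does not declare, with a modest and conditional effect on interpretation. The tabulated AESI percentages refer to no stated week. Categories with fewer than 5 events in each arm have no censoring-adjusted, time-based summary of patient risk, and the exposure-adjusted count does not replace it.

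Under the planned drop-out, the crude figure is close to the Week 52 risk and about 21 to 27% below the Week 72 risk. Between arms, bias requires discontinuation or withdrawal to differ: a crude ratio of about 0.85 to 0.92 at 30% versus 10%, and about 0.78 to 0.88 at 40% versus 10%, when the true ratio is 1. The arm that leaves earlier looks safer.

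These sizes rest on an assumed constant hazard, equal in both arms, and on assumed imbalances. Events that cluster soon after first dosing would show less of either effect. A reader might also infer that K-M would remove any bias; it does so only if censoring is non-informative. The change should be made, but it does not threaten the trial's main conclusions.

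**What to change.** In SAP 2.4.5.1:

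1. For each AESI category with any event, restore K-M cumulative incidence by arm, with 95% CI and number at risk, at the protocol's Weeks 1, 4, 12, 24, 52 and 72. Censor at the earlier of last contact and the end of the treatment-emergent period.
2. Make Weeks 24 and 52 the main time points, and footnote that Week 72 rests on about 15 patients per arm.
3. Keep the threshold of 5 events for plots only, and record that restriction in SAP 1.5.
4. Define the denominator of the exposure-adjusted count as time in the treatment-emergent window, so that it matches the events counted.

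If the sponsor prefers not to restore the estimates, SAP 1.5 should list their removal and give the reason.

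The cost is one more table per AESI category, from data already collected. The estimates will be imprecise for sparse categories and at Week 72, and are valid only under non-informative censoring.

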2.4.5.2 Deaths

The following summaries of deaths will be generated for the safety population.

- Number (%) of patients who died by study period (on-study, on-treatment, post-study)
- TEAEs leading to death (death as an outcome on the adverse event case report form page as reported by the Investigator) by primary SOC and PT
- Listing of all AEs leading to death

In addition, summary of deaths in non-randomized patients or randomized but not treated patients may be generated.

2.4.5.3 Analyses of laboratory variables

The summary statistics (including number, mean, median, Q1, Q3, standard deviation, minimum and maximum) of all laboratory variables (central laboratory values and changes from baseline) will be calculated for each visit or study assessment (baseline, each post-baseline time point and last on-treatment) by treatment group. For each continuous parameter listed in [Section 2.1.4.3](#), mean changes from baseline with the corresponding standard error will be plotted over time in each treatment group. This section will be organized by biological function as specified in [Section 2.1.4.3](#).

The incidence of PCSAs (list provided in [Appendix A](#)) at any time during the TEAE period will be summarized by biological function and treatment group whatever the baseline level and/or according to the following baseline status categories:

- Normal/missing
- Abnormal according to PCSA criterion or criteria

For parameters for which no PCSA criteria are defined, similar table(s) using the normal range will be provided.

Laboratory measurements obtained at either scheduled or unscheduled visits will be used in analyses of PCSA. In addition, both centralized and local test results will be used. Centralized data will be used preferentially to the local measures in the analysis when several measurements are performed on the same date and at the same time for a given laboratory test.

Listings will be provided with flags indicating the out of range values as well as the PCSA values.

Potential drug-induced liver injury

The liver function tests, namely AST, ALT, alkaline phosphatase and total bilirubin will be used to assess possible drug-induced liver toxicity. The proportion of patients with PCSA values at any post-baseline visit will also be displayed by duration of exposure for each treatment group.

A graph of distribution of peak values of ALT versus peak values of total bilirubin will also be presented on a logarithmic scale. The graph will be divided into 4 quadrants with a vertical line corresponding to 3 x ULN for ALT and a horizontal line corresponding to 2 x ULN for total bilirubin.

Listing of selected laboratory parameters for possible Hy's law cases identified by treatment group (eg, patients with any elevated ALT >3 x ULN, and associated with an increase in bilirubin ≥ 2 x ULN) will be provided.

The normalization (to ≤ 1 x ULN) or return to baseline (if baseline is >ULN) of elevated liver function tests will be summarized by categories of elevation (>3 x ULN, >5 x ULN, >10 x ULN, >20 x ULN for ALT and AST, >1.5 x ULN for alkaline phosphatase, and >1.5 x ULN and >2 x ULN for total bilirubin) with the following categories of normalization: never normalized, normalized despite treatment continuation of IMP, or normalized after IMP discontinuation. A patient will be counted only under the maximum elevation category.

Change in Blood Eosinophil

Absolute and percent mean (median) change from baseline in eosinophil count will be summarized and plotted over time in each treatment group for patients with baseline blood eosinophil <0.25 Giga/L and patients with baseline blood eosinophil ≥ 0.25 Giga/L.

